4.2 Inclusion and Exclusion Criteria

Eligible participants will be identified from the wider BABY cohort over a 12 month period. All women approached to participate in the BABY PaNDA study will have already consented to take part in the wider BABY cohort.

4.2.1 Inclusion criteria

Women will be approached to participate in BABY PaNDA if they have already consented to the BABY cohort *and* have consented to be contacted again *and* are less than 20 weeks pregnant; *and* are aged 16 years and above; *and* are currently living in one of the research areas (York, Hull, Harrogate, or Scunthorpe & Goole).

4.2.2 Exclusion criteria

Women will only be excluded if they are non-English speaking. Women with literacy difficulties will not be excluded; in these cases all study information and questionnaires will be read out to them. Women who return a completed consent form will not be eligible to take part in the study if they are over 24 weeks pregnant at the time the consent form is received.

We feel the option of providing translated versions of all study questionnaires to women participants with literacy difficulties is not appropriate within the context of this study. The English and translated versions could not be considered equivalent and therefore could not be combined in statistical analyses. We anticipate too few numbers of women participants who would require translated versions of the questionnaires to enable us to validate these.

4.3 Recruitment & Consent

Recruitment will take place over a 14 month period across four study sites – York, Hull, Harrogate, and Scunthorpe & Goole. Recruiting from these geographically and demographically distinct health economies will help us to ensure the results of epidemiological insights from this study are generalisable to the wider NHS.

Approximately 40% of eligible women are currently consenting to the BABY cohort in York. Of 800 women recruited to the cohort by the end of 2012, around 50% gave consent before 18 weeks of pregnancy. The recent pilot validation study (17) reported a consent rate of 58% from the Born in Bradford (BiBs) birth cohort. We feel a 14 month recruitment period is therefore realistic to achieve our recruitment target.

An information pack will be sent at approximately 15-18 weeks gestation to women who have consented to the BABY cohort by that stage of their pregnancy and who have also given their consent to be contacted again. The information pack will contain an invitation letter, a summary information sheet which describes the key aspects of the study, a participant information sheet which provides full details of the study, a consent form and a pre-paid stamped-addressed return envelope. The summary information sheet and the participant information sheet will provide contact details for the Project Manager in the event a woman requests further information about the study. Sending the information pack at 15 to 18 weeks gestation should provide sufficient time for women to make an informed decision about whether they want to take part in BABY PaNDA (and to contact the research team if they have any questions) and for the researcher to organise the first interview at 20 weeks gestation following receipt of a completed consent form. The BaBY PaNDA summary information sheet will also be made available to women who may be interested in taking part in the BaBY cohort study either during visits to antenatal clinic and/or during contact with members of the BaBY study team.

Women who have not returned a completed consent form after two weeks of being sent the information pack may be contacted by a member of the BaBY study team to discuss the BaBY PaNDA study and to provide them with an opportunity to ask any questions they may have about the study. Women will be contacted by telephone, email or text, depending on the method(s) of contact they have provided during consent to the BaBY study. Interested women who are contacted following receipt of a BaBY PaNDA information pack will still need to complete the consent form and return this to the BaBY PaNDA research team.

All general practitioners (GPs) in the BABY cohort areas are sent information about the BABY cohort study before recruitment in their area begins. This material will additionally include information about the BABY PaNDA study. Information about the BaBY and BaBY PaNDA studies will also be visible in locations where pregnant women attend as part of their maternity care pathway (e.g. as posters and on 'BaBY TV' in antenatal clinics, as posters in Children's Centres, GP surgeries) and will be provided online (www.bornbredyorks.org). Hospital and community midwives across each recruitment site may also discuss the BaBY and BaBY PaNDA studies with pregnant women under their care. Information about BaBY and BaBY PaNDA may also be promoted through press releases, local press activities and through appropriate local advertising avenues (e.g. online information and/or support groups, local magazines). After consent has been received, women will be contacted by a member of the local research team to arrange the 20 week pregnancy assessment. At this point the researcher will confirm that women understand why the research is being conducted and what they will be asked to do during the study; this will provide a further opportunity for women to ask any questions they may have. The 20 week assessment will take place at a time and location of the woman's choice – expected locations include the local hospital maternity unit (for example, at the time of the woman's 20 week scan appointment), health and social care locations in the community, the woman's home, at the University of York or elsewhere.

After consent has been received, one copy of the woman's consent form will be sent to the women's GP along with a letter informing them that their patient has been included in the study, and one copy of the consent form will be kept by the woman. A BaBY PaNDA study sticker will also be placed in the woman's maternity records by a member of the maternity research team.

4.4 Outcome Measures & Data Collection

Data will be collected from all women at three time points during the course of the study:

Stage 1: Prenatal (20 weeks pregnancy)

Stage 2: Postnatal (3-4 months post-birth)

Stage 3: Follow-up (1 year post-birth)

The following outcomes measures will be collected:

Depression screening measures:

 NICE ultra-brief depression screening questions (13) and the additional help question (27) will be administered as a self-report questionnaire at stages 1, 2 & 3.

A "yes" or "no" response is required for each of the two screening questions (see Box 1). A "yes" response to either of these screening

questions will be considered a 'positive screen' for perinatal depression and will require a "yes", "yes, but not today", or "no" response to the additional help question to enquire if help is needed (see Box 1). If any women respond "yes" to this help question they will be advised to speak with their GP and that information about perinatal depression can be found on the NHS website (www.nhs.uk). The two screening questions have been validated in primary care samples (13, 27) and other clinical populations (28-30). The two screening questions have since been validated in a limited perinatal population; this study reported 100% sensitivity at both the antenatal and the postnatal stage, and specificity of 68% at the antenatal stage and 65% at the postnatal stage. Additionally, they showed that for positive screens, the use of the additional help question improved the specificity and the ability to rule in depression (17).

 Edinburgh Postnatal Depression Scale (EPDS) (31) will be administered as a self-report questionnaire at stages 1, 2 & 3.

The EPDS is a 10-item self-report questionnaire and is currently the most utilised self-report measure to detect postnatal depression in maternity and child services (32). Each item is scored on a 4-point scale (0-3) with a total score ranging from 0-30. Using a cut-off score of ≥13 to detect major depression in the postnatal period, the EPDS has been shown to have a sensitivity of 91% and a specificity of 91%.

Diagnostic gold standard:

• The Clinical Interview Schedule – Revised (CIS-R) will be administered as a self-report computer-based assessment at stages 1, 2 & 3.

The CIS-R is a diagnostic gold standard, lay-administered computerbased interview schedule which assesses the presence or absence of depression and other common mental health disorders according to ICD-10 criteria (33, 34). It has been validated in primary care samples, has been shown to have good reliability (33) and has been used in national psychiatric morbidity surveys (35). It has also been shown to have comparable validity when delivered over the telephone (36).

Secondary outcome measures

Minimal biographic and demographic information will be collected at stage 1 only.

The following outcomes measures will each by administered as self-report questionnaires:

- PHQ-9 (Patient Health Questionnaire) (37) at stages 1, 2 & 3: a 9-item questionnaire which records the core symptoms of depression and has been validated in a primary care population (38). It is widely used in primary care for all cases of depression
- *GAD-7* at stages 1, 2 & 3: a 7-item questionnaire which assesses symptoms of anxiety (39)
- *PHQ-15* at stages 1, 2 & 3: a 15-item questionnaire which assesses somatoform complaints (40)
- *SF-12* at stages 1, 2 and 3: a 12-item questionnaire which assesses health-related quality of life (41)
- EQ5D at stages 1, 2 & 3: a 5-item questionnaire which assesses health-state utility (42)
- *Resource-use questionnaire* at stages 1, 2, & 3: a detailed questionnaire used to capture service-use data.
- Acceptability Survey at stages 1 & 2: a self-report tool designed to assess the acceptability of the EPDS (12). This has since been adapted to include an assessment of the acceptability of the NICE ultra-brief depression screening questions (17) and further adapted for the purposes of this study (see section 4.1.3).

In addition, the researcher administering the NICE ultra-brief depression screening questions and the EPDS at stages 1 and 2 will record the time it

takes for them to administer each screening questionnaire when completed face-to-face or over the telephone. These data will feed into the cost-effectiveness evaluation.

Method of data collection

Outcome measures will be obtained during face-to-face interviews at stages 1 & 2; if women are unable to attend a face-to-face interview the data will be collected by telephone, or by a combination of telephone (diagnostic gold standard – CIS-R) and post (self-report questionnaires). Outcome measures at stage 3 will be obtained by telephone, or by online completion (via a secure University of York website) or by a combination of telephone (diagnostic gold standard - CIS-R) and post (self-report questionnaires); face-to-face interviews will be arranged for those women who specifically request this method of data collection. Interviews at stages 1 to 3 will last no longer than 60 minutes.

Outcome measures will be administered within the same interview by one researcher. The depression screening questionnaires will be administered before the diagnostic gold standard (CIS-R). For instances where it is not possible to administer the depression screening questionnaires and the CIS-R within the same interview, the CIS-R will be administered within two weeks of women completing the depression screening questionnaires. Any issues which may arise during interviews will be documented in order to provide information about potential sources of bias. To ensure blinding of outcome results between stages, interviews will be conducted by different researchers, except where it is more appropriate / sensitive for the same researcher to conduct each interview.

Face-to-face interviews will take place at a time and location of the woman's choice (expected locations include local hospital maternity units, health and social care locations in the community, the woman's home, at the University of York or elsewhere). All data will be collected by a member of the study research team. All researchers will follow a lone worker policy when conducting face-to-face interviews.

Protocols will be in place for those women identified as at risk of depression and/or anxiety and/or self-harm/suicide, and for the identification and reporting of adverse events (see Appendices 3 and 4, and section 8).

4.6 Withdrawal

Withdrawal can occur at any stage during the study following consent at the request of the woman. Data will be retained for all women up to the date of withdrawal, unless they specifically request for their information to be removed. All personal information will be destroyed following the request to withdraw from the study.

Following consent to the study, any women who subsequently suffer a fetal loss (such as miscarriage, termination of pregnancy, stillbirth or neonatal death) will not automatically be withdrawn from the study. However, women will be contacted by letter by a member of the BaBY PaNDA study team to offer condolences , thank them for their interest in the study and to provide them with the opportunity to remain in the study should they wish to do so. Women who do not respond to this letter will not be contacted again by the BaBY PaNDA study team. Data will be retained for these women up to the date of the event, unless they specifically request for their information to be removed. Robust protocols will be in place via the BABY cohort (and in liaison with clinical teams using routine NHS systems at each study site) which will act to alert the BABY PaNDA study team of such events.

5 Statistical Considerations

5.1 Sample size calculation

We will aim to recruit 379 pregnant women. This sample size calculation is based on a previously developed method (43), for an expected sensitivity of 95% and a minimal acceptable lower 95% confidence interval (CI) of more than 0.80 with 0.95 probability, where estimated prevalence of prenatal and postnatal depression is 20%. Attrition is estimated at 34% based on a previous pilot validation study of the NICE ultra-brief depression screening questions to identify perinatal depression in a limited perinatal population (17).

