The two depression screening tools - the NICE ultra-brief depression screening questions and the EPDS - will be validated against a WHO (World Health Organisation) diagnostic gold standard clinical assessment of depression (International Classification of Disease, ICD-10) at two stages - 20 weeks pregnancy and 3-4 months post-birth. By cross-validating the diagnostic gold standard against scores on the two depression screening tools at these two time points in the perinatal care pathway we will be able to assess the diagnostic accuracy of these tools in terms of false positives, false negatives and true negative results. This in turn will yield measures of sensitivity, specificity and positive and negative likelihood ratios (with 95% confidence intervals) and hence the diagnostic utility of the depression screening tools. This validation method will also permit us to judge the temporal stability of positive and negative screens between pre- and post-birth and the natural history of screen-positive depression across the perinatal period. This will also enable us to ascertain the persistence of early screens in predicting longer-term problems. This will provide important information on the nature of the relationship between depression before and after birth.

A diagnostic assessment of co-morbidity will be made in two ways: by using previously validated questionnaires and by using the WHO diagnostic gold standard structured interview to ascertain the presence of common mental health problems, such as anxiety disorders and somatoform complaints (physical symptoms with a lower probability of physical pathology). An assessment of psychological co-morbidity will be made at three time points during pregnancy and early motherhood: 20 weeks pregnancy, 3-4 months post-birth and 1 year post-birth. This will allow us to examine the co-existence of depressive symptoms alongside other common mental health problems during the perinatal period. This will inform the delivery of psychosocial treatments by mental health practitioners to take account of other common mental health problems, such as anxiety and somatic complaints.

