5.2 Data Analysis

5.2.1 Quantitative data analysis

The sensitivity, specificity and predictive values of the NICE ultra-brief depression screening questions and the EPDS will be calculated at 20 weeks of pregnancy and 3-4 months post-birth with two-by-two contingency tables against the ICD-10 diagnostic gold standard. Associated 95% confidence intervals will also be calculated for each estimate at each time point. Receiver Operating Characteristic (ROC) curves will also be constructed to determine performance characteristics for each depression measure. Based on the predictive properties of the depression screening measures, optimum times for screening will be identified. The numbers of women with indeterminate and/or missing results (if available). The baseline characteristics of women with indeterminate and/or missing results (if available). The baseline characteristics of women with indeterminate and/or missing results will be compared to those who have complete data using descriptive statistics. A logistic regression model will also be used to identify predictors of non-response.

McNemars test will be used to explore the temporal stability of responses between 20 weeks of pregnancy and 3-4 months post-birth for each of the depression screening measures. The co-existence of depressive symptoms alongside other common mental health problems will be summarised descriptively (mean, standard deviation, median, minimum and maximum and frequency and percentages at established cut points) at each time-point.

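### The 0.95 probability in 5.1 fits a one-sided exact limit with 50 cases fixed; for the lower end of an ordinary two-sided 95% interval after attrition it is about 0.90

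*Protocol*

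**What the plan says.** Protocol 5.1 states the target ("We will aim to recruit 379 pregnant women") and the precision criterion: "a minimal acceptable lower 95% confidence interval (CI) of more than 0.80 with 0.95 probability". The inputs are an expected sensitivity of 95%, a prevalence of 20% for both prenatal and postnatal depression, and a loss of 34% ("Attrition is estimated at 34% based on a previous pilot validation study"). The method is cited, not described: "This sample size calculation is based on a previously developed method (43"). Section 5.1 does not say whether the lower limit is one-sided or two-sided, which interval is meant, how many cases are expected, or at which stage the attrition applies.

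For the analysis, section 5.2.1 says, of sensitivity, specificity and predictive values at 20 weeks and at 3-4 months: "Associated 95% confidence intervals will also be calculated for each estimate at each time point". Section 4.1.2 likewise promises "measures of sensitivity, specificity and positive and negative likelihood ratios (with 95% confidence intervals"). Neither section mentions a one-sided limit.

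**The concern.** The probability in 5.1 is the only operating property that the protocol states for its accuracy analyses. A reader will apply the 0.80 benchmark to the lower end of the 95% interval that the study publishes. By ordinary usage that interval is two-sided, so its lower end cuts off 2.5%. If the planning limit cut off 5%, the stated 0.95 belongs to a different and easier limit than the one to be reported.

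The calculation also fixes the number of depressed women at its expected value, although the study recruits women and the number of cases among them is random. What is at stake is an overstated chance of meeting the benchmark. The recruitment target is not in question.

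**Working it through.** **Inputs (all from Protocol 5.1).** Recruited 379; attrition 0.34; prevalence 0.20; true sensitivity 0.95; benchmark 0.80; stated probability 0.95.

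**Step 1: reproduce the target.** For *n* cases, find the smallest number detected, *x*, whose lower limit exceeds 0.80. Then compute P(X ≥ *x*) with X ~ Binomial(*n*, 0.95).

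- With a one-sided exact (Clopper-Pearson) 5% limit, the first *n* to reach 0.95 is 50.
- At *n* = 50, 45/50 gives a limit of 0.8012, and P(X ≥ 45) = 0.962.
- At *n* = 49, 45 are again needed, and the probability is only 0.903.
- Women analysed: 50 / 0.20 = 250. Women recruited: 250 / 0.66 = 378.8, rounded up to 379.

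The match is exact. In the other direction, 379 × 0.66 = 250 and 250 × 0.20 = 50.

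**Step 2: use the lower end of a two-sided 95% interval, 50 cases fixed.**

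| Interval | Lower limit, 45/50 | Detections needed | Probability |
|---|---|---|---|
| Exact | 0.782 | 46 | 0.896 |
| Wilson | 0.786 | 46 | 0.896 |
| Jeffreys | 0.795 | 46 | 0.896 |
| Wald | 0.817 | 45 | 0.962 |

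For 46/50 the exact limit is 0.808 and the Wilson limit 0.812, so both pass. One more detection is required, and the probability drops from P(X ≥ 45) = 0.962 to P(X ≥ 46) = 0.896. The chance of missing the benchmark is then 1 − 0.896 = 0.104, about twice the stated 0.05.

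**Step 3: let the number of cases vary.** Take cases K ~ Binomial(250, 0.20), so that P(K < 50) = 0.475, and average the Step 1 and Step 2 probabilities over K.

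| Limit | Probability, 250 women |
|---|---|
| One-sided exact | 0.928 |
| Two-sided exact | 0.868 |
| Two-sided Wilson | 0.884 |
| Two-sided Jeffreys | 0.911 |
| Two-sided Wald | 0.963 |

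Leaving Wald aside, the two-sided miss risk is 1 − 0.911 = 0.089 to 1 − 0.868 = 0.132.

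**Step 4: the 20-week analysis.** Section 5.1 does not say when the 34% is lost. If all of it falls after the 20-week assessment (an assumption), that stage has 379 × 0.20 = 75.8, about 76 cases. The two-sided exact probability is then 0.987 with the count fixed and 0.977 with K ~ Binomial(379, 0.20). If instead all the loss comes before that assessment, the stage has 50 cases and Steps 2 and 3 apply. The range is therefore 50 to 76 cases.

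**The case against.** The strongest reply is that nothing is miscalculated. Section 5.1 speaks of a lower 95% limit, which can be read as a one-sided bound. On that reading the inputs return 379 exactly and the stated 0.95 is met. This stands as far as the target goes. A reader might infer that 379 is an arithmetic error, and the documents do not support that. But 5.1 does not say that the limit is one-sided, and 4.1.2 and 5.2.1 promise to report 95% intervals without that qualification.

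Four further points have force.

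- **Fifty is not a lone lucky value.** A reader might infer from the drop at 49 cases that the one-sided figure holds at 50 only. It does not: the one-sided exact limit also reaches 0.95 at 51 to 53 cases (0.959, 0.956, 0.952) and from 57 upward. It dips to 0.948-0.940 at 54 to 56.
- **The interval type is unnamed, and that can be left to a statistical analysis plan.** A two-sided Wald interval would keep 0.96. But a plan that chose exact, Wilson or Jeffreys would leave the 0.95 in 5.1 untrue for the 250-woman analysis. The value 0.87 belongs to the exact interval only.
- **Dividing required cases by prevalence is ordinary planning practice,** and 5.1 does not claim an unconditional probability. That is fair, so the varying-count figures are a supplement. The drop to about 0.90 does not depend on them.
- **The 0.80 is a planning criterion.** No section makes it a success rule, and no study conclusion turns on it. The shortfall also assumes a true sensitivity of exactly 95%: at 96% the two-sided exact probability with 50 cases is already 0.951. This limits the consequence, but 95% is the protocol's own input.

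A reader might also infer that the whole study falls short. Step 4 shows that this is not supported for the 20-week analysis.

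**Conclusion.** The point holds as a mismatch between the limit behind the stated probability and the intervals to be reported. At the protocol's own inputs, the sample left after attrition gives about 0.90 for two-sided exact, Wilson or Jeffreys intervals, against the stated 0.95. With a varying case count the figures are 0.87, 0.88 and 0.91 for exact, Wilson and Jeffreys, and even the one-sided exact limit gives 0.93.

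This rests on three assumptions: the reported 95% intervals are two-sided, they are not Wald intervals, and true sensitivity is exactly 95%. It bears on the 3-4 month analysis, which matters because postnatal validation is part of the first research objective in section 3 and 5.1 applies its prevalence to postnatal depression too. The 20-week analysis exceeds 0.95 if the loss comes after it. The consequence is a stated assurance that is modestly too favourable. It does not make the sample size wrong.

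**What to change.** Restate 5.1 and leave the target of 379 as it is. Either of two wordings would do:

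- **(a) Match the reported interval.** With 50 expected cases after attrition, the lower limit of the two-sided 95% confidence interval (exact or Wilson) exceeds 0.80 with probability about 0.90, or 0.87-0.88 allowing for variation in the number of cases.
- **(b) Keep the one-sided benchmark.** Say that 0.80 is judged against a one-sided exact 95% lower limit, report that limit beside the two-sided interval, and give the probability as 0.96 with 50 cases fixed, or about 0.93 with a varying count.

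In either case, say that the figure refers to the analysis after attrition.

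The cost is one or two sentences and a slightly less favourable stated figure. Option (b) adds one reported limit per sensitivity estimate. Neither option needs more women or a change of design.
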